##### **6.6.4.1. Immune related adverse events**

The criteria for classification of an adverse event as an irAE is described in Appendix 1. The frequency (number and percentage) of participants with each of the following will be presented for irAEs, by treatment arm in Cohort A and by Cohorts B1 and B2, if applicable:

- irAEs leading to death, by Cluster and PT (Cohort A only)
- irAEs, by Cluster, PT, and worst Grade
- irAEs, Any Grade and Grade  $\geq 3$ , by Cluster and PT (Cohort A only)
- irAEs leading to discontinuation of PF-06801591, by Cluster and PT
- irAEs leading to discontinuation of BCG, by Cluster and PT (Cohort A only)
- irAEs leading to discontinuation of all study drugs, by Cluster and PT (Cohort A only)
- Serious irAEs, by Cluster and PT

The listing of all irAEs will also be provided with the relevant information with a flag for irAEs with onset outside of the on-treatment period for irAE (i.e., irAEs not meeting the programmatic criteria in Step 2 as outlined in Table 25 of Appendix 1)

The frequency (number and percentage) of participants with potential irAEs (i.e., AEs meeting the programmatic criteria Step 1 and Step 2 outlined in Table 25 of Appendix 1) will also be presented by treatment arm in Cohort A and by Cohorts B1 and B2.

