## **7. INTERIM ANALYSES (COHORT A ONLY)**

### **7.1. Introduction**

The goals of the interim analyses are to allow early stopping of treatment arm(s) for futility or efficacy.

Prior to protocol amendment 5, two interim (IA1(futility only) and IA2) and final (FA) analyses were planned for the primary endpoint of Cohort A. IA1 for EFS was conducted after 658 participants were randomized to Cohort A for all 3 arms combined. As IA1 was for futility only, no alpha was spent at IA1.

Based on protocol amendment 5, the IA2 will be removed, and the FA for EFS based on a calendar-based data cut-off date will be conducted. Randomization to Cohort A was completed on 16 November 2021 and the EFS FA data cut-off date will be set to allow for approximately 3 years of follow-up after last randomized participant.

The interim efficacy analysis of OS will be performed as described in Sections 5.1.1 and 5.1.2 using the methodology described in Section 6.2.2.2.

As this is an open-label randomized study, the treatment is unblinded on participant level. However, the aggregate/cumulative data summaries by treatment arm will be unavailable to the study team and the external investigators until the database snapshot for the primary analysis.

Unblinded results from the interim futility analysis for EFS will not be communicated to the Sponsor's clinical team or to any party involved in the study conduct (apart from the independent statistician and E-DMC members) until the E-DMC has determined that either (i) EFS analysis has crossed the pre-specified boundary for efficacy or (ii) the study needs to be terminated due to any cause, including futility or safety reasons. Further details will be described in the E-DMC charter.

At the time of final EFS analyses, all participants will continue to be followed for OS until the final OS analysis (approximately 5 years after the last participant is randomized).

Based on PA5, since EDMC review of interim efficacy data (IA2) is no longer applicable, the study team will be unblinded to aggregate/cumulative data summaries by treatment arm at the time of FA for EFS. No additional EDMC activities are foreseen after the FA for EFS.

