**Table 25. Case Definition for irAEs**

Step	Selection Criteria	
1	Adverse Event (AE) selected based on a list of pre-specified MeDRA PTs within clusters. These are included in the SRP. If AE matches the list, then it is included in the next step.	
2	AE onset on or after the first dose of study drug and on or before 90 days after last dose of study treatment.	This is regardless of start of new anti-cancer drug therapy and regardless of TEAE classifications.
3	AE treated with corticosteroids or other immunosuppressant therapy. For endocrinopathies only: AE required hormone replacement.	Look in the conmed pages for AEs where concomitant medications match any of the following A) conmed ATC code is in (H02A, H02B, D07, A01AC, S01BA, S01BB, L04AA, L04AB, L04AC, L04AD, L04AX, A07EA) and AE PT is in any of the irAE clusters. B) conmed ATC code is in (H03A, H03B) and AE PT is in one of the irAE clusters associated with “Immune-mediated endocrinopathies: Thyroid disorders” C) conmed ATC code is A10A and AE PT is in the irAE cluster associated with “Immune-mediated endocrinopathies: Type I Diabetes Mellitus”
4	4A) AE has no clear alternative etiology other than the immune-mediated etiology. OR 4B) AE has a histopathology / biopsy consistent with immune-mediated event.	Steps 4A) and 4B) are assessed by the clinical team based on medical review of the data available in the CRF and SAE report (if applicable). Steps 4A) and 4B) are not completed programmatically.

The data set associated with irAEs may be further refined based on medical review. The final data set including any changes based on medical review will be the basis of the irAE analyses.

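### The last steps of the irAE definition are a clinical judgement made with each participant's treatment known and no stated masking or lock, so the by-arm irAE comparison may be affected by arm-aware attribution

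*SAP*

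**What the plan says.** SAP Appendix 1, Table 25, checks each step only for events that passed the one before. Step 1 is a list of preferred terms, Step 2 an onset window reaching 90 days after the last dose, and Step 3 a match to concomitant medication codes (corticosteroids, other immunosuppressants, or hormone replacement for endocrinopathies). Step 4 is met by either of two routes. Route 4A is that the "AE has no clear alternative etiology other than the immune-mediated etiology"; route 4B is consistent histopathology or biopsy. On who decides, the table says: "Steps 4A) and 4B) are assessed by the clinical team based on medical review of the data available in the CRF", together with the SAE report where there is one.

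The text after the table adds: "The data set associated with irAEs may be further refined based on medical review". It then says: "The final data set including any changes based on medical review will be the basis of the irAE analyses".

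SAP 7.1 states: "As this is an open-label randomized study, the treatment is unblinded on participant level". It then restricts access to one kind of information: "the aggregate/cumulative data summaries by treatment arm will be unavailable to the study team and the external investigators until the database snapshot". Protocol 6.3 also lets the sponsor review unblinded patient-level data for cleaning.

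SAP 6.6.4.1 presents irAEs by Cohort A arm, by cluster, preferred term and grade, and for fatal events, serious events and discontinuations. It also plans the frequency by arm of "participants with potential irAEs (i.e., AEs meeting the programmatic criteria Step 1 and Step 2 outlined" in Table 25. SAP 6.6.1 has the Step 1 term list finalised before database lock. No similar commitment is given for Step 4 or the later refinement.

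**The concern.** Route 4A asks whether something other than an immune mechanism explains the event. Whether the participant received an anti-PD-1 antibody bears directly on that answer, and the people answering can know it. Withholding aggregate summaries does not hide the arm of the case under review.

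IrAEs are one of two kinds of AE of special interest in the SAP. The other, injection site reactions related to PF-06801591, cannot occur in Arm C. IrAEs are therefore the AESI for which Arm C can supply a randomised background rate. If the share of events kept at Step 4 depends on knowledge of arm, the difference between arms in the final irAE tables reflects the review process as well as the drug. For efficacy, the SAP adds central-review checks on investigator-assessed EFS events and complete responses (6.2.2.3 and 6.2.2.5). It describes no comparable check on the irAE judgement.

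**Working it through.** The plan states no irAE rate, test or margin, so there is no figure of its own to reproduce. The check has two parts.

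**1. How far unequal retention could move the comparison.** Let p be the share of an arm meeting Steps 1 to 3 and r the share of those kept after review. The reported rate is p × r. The reported ratio of Arm A to Arm C is (pA/pC) × (rA/rC), so review distorts the ratio by rA/rC. All values of p and r below are assumptions.

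With p equal in the two arms, any difference comes from review alone:

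| Kept in A / C | Ratio rA/rC | Difference at p = 5% | at p = 10% | at p = 20% |
|---|---|---|---|---|
| 90% / 90% | 1.00 | 0 | 0 | 0 |
| 90% / 70% | 1.29 | +1 point | +2 | +4 |
| 90% / 50% | 1.80 | +2 | +4 | +8 |
| 70% / 90% | 0.78 | −1 | −2 | −4 |

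For scale, 1056 randomised at 1:1:1 (protocol 4.1.1) is 1056/3 = 352 per arm. At p = 10% with 90%/70% kept, that is 31.7 participants against 24.6.

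With a real excess, say 15% in Arm A and 5% in Arm C:
- 90% kept in both: 13.5% against 4.5%, difference 9.0 points, ratio 3.0.
- 90% / 50%: 13.5% against 2.5%, difference 11.0 points, ratio 5.4.
- 70% / 90%: 10.5% against 4.5%, difference 6.0 points, ratio 2.3.

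The distortion can run either way.

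**2. Whether the planned tables would reveal it.** For each arm, write N12 for the number passing Steps 1 and 2, N123 for Steps 1 to 3, N1234 after Step 4, and Nfinal after refinement. Then

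N12 − Nfinal = (N12 − N123) + (N123 − N1234) + (N1234 − Nfinal).

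The SAP plans N12 and Nfinal by arm. It plans neither N123 nor N1234. The gap a reader would see therefore mixes the medication filter, the Step 4 judgement and the refinement, and cannot be separated. N12 also has no stated breakdown by cluster or grade, so it cannot be set against the final tables at that level. Adding N123 and N1234 identifies all three terms from data already collected.

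**The case against.** Several points on the other side stand.

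- **Direction is not fixed.** A reader might infer that Arm C events will be screened out and the excess in Arms A and B inflated. The documents do not support that. BCG is given in all three arms, and protocol 2.3 attributes most BCG reactions to immune stimulation. A reviewer could credit an Arm A event to BCG, or keep an Arm C event as immune-mediated. Route 4B also rests on a documented finding.
- **Unequal retention is not in itself bias.** The irAE category is an attribution category, and some Arm C events may properly fail Step 4. Counts by step show how much review removed, not whether it was right to.
- **Unadjudicated comparisons exist.** TEAEs by term and worst grade (SAP 6.6.1.1) and SAEs (6.6.3) are tabulated by arm with no Step 4 filter, so the Arm C background is not lost from the report. These tables stop 30 days after the last dose or at new anti-cancer drug therapy, whereas Step 2 runs to 90 days regardless of new therapy.
- **Step 3 is not free of judgement.** Its input is an open-label investigator's decision to give steroids, immunosuppressants or hormones, and protocol 10.13 directs such treatment for many suspected irAEs. A reader might take a Steps 1 to 3 count as fully objective; it is free only of Step 4 adjudication.
- **Nothing inferential is at stake.** Protocol 9.4.2 makes the safety analysis descriptive.
- **The Safety Review Plan was not supplied.** It may already mask the review.

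None of these supplies what is missing: a stated safeguard for the judgement, or a table that isolates its effect.

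**Conclusion.** The point holds as a risk in the plan as written. The final irAE classification depends on judgement by a team that can know each participant's treatment, the later refinement has no stated criteria, and neither document describes masking or locking. The between-arm irAE comparison may be affected. The documents do not show that it is biased, and they fix neither size nor direction. The assumed scenarios with equal Steps 1 to 3 rates run from −4 to +8 percentage points and show only what unequal retention could do. The Steps 1 and 2 count and the TEAE and SAE tables mitigate the risk in part, but cannot show what medical review removed in each arm. No hypothesis test or alpha is touched. The conclusion assumes that the Safety Review Plan does not already provide masking. This is an inexpensive improvement worth making, and it does not threaten the trial's main conclusions.

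**What to change.** In SAP Appendix 1, state that:
- Step 4 and any later refinement are done from listings with treatment arm and investigator causality to PF-06801591 masked where feasible. Event timing relative to study treatment should stay visible, because it informs etiology; masking every dosing and action-taken field would go too far.
- The reason for each exclusion or change is recorded.
- Classifications are locked before arm is merged back.

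If the Safety Review Plan already provides this, a sentence saying so is enough.

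In SAP 6.6.4.1, add irAEs meeting Steps 1 to 3 by arm, cluster and worst grade, with the number per arm removed at Step 4 and the number changed by later refinement. Describe the table as free of Step 4 adjudication, not of all judgement.

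The cost is SAP wording, a masked review listing and one extra table, with no new data or staff. Masking will be imperfect where narratives or drug-specific fields reveal the arm. If unmasked review has already taken place, the extra table can still be produced and still shows what review changed in each arm.

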## Appendix 2. List of Abbreviations

Abbreviation	Term
ADA	anti-drug antibodies
AE	adverse event
AESI	adverse events of special interest
ALP	alkaline phosphatase
ALT	alanine aminotransferase
AST	aspartate aminotransferase
ATC	anatomical therapeutic chemical
BCG	bacille calmette guérin
BLQ	below the level of quantification
bpm	beats per minute
CD8	cluster of differentiation-8
CI	confidence interval
CIS	carcinoma in situ
CR	complete response
CRF	case report form
CSR	clinical study report
CT	computed tomography
CTCAE	common terminology criteria for adverse events
C max	maximum observed concentration
C trough	concentration at predose/trough
CV	coefficient of variation
DNA	deoxyribonucleic acid
DoCR	duration of complete response
DSS	disease-specific survival
ECG	electrocardiogram
ECOG	Eastern Cooperative Oncology Group
eCRF	electronic case report form
eDISH	evaluation of drug-induced serious hepatotoxicity
EFS	event-free survival
EORTC	European Organisation for Research and Treatment of Cancer
EORTC-GU	EORTC-Genito-Urinary
EOT	end of treatment
EQ-5D-5L	EuroQol 5 Dimensions, 5-Level
FA	final analyses
FAS	Full analysis set
FFPE	formalin-fixed paraffin-embedded
GCP	Good clinical practice

Abbreviation	Term
HR	hazard ratio
IA	interim analysis
ICD	informed consent document
IgA	immunoglobulin A
IgG	immunoglobulin G
irAE	immune-related adverse event
IRT	interactive response technology
LLQ	lower limit of quantitation
LLN	Lower limit of normal
MNT	maintenance
MRI	magnetic resonance imaging
MWPC	meaningful within person change
N+	lymph node positive disease
NAb	neutralizing antibodies
NCI	National Cancer Institute
ND	not done
NMIBC	non-muscle invasive bladder cancer
NR	Not reached
NS	no sample
OS	overall survival
PD	progressive disease
PGIC	patient global impression of change
PGIS	patient global impression of severity
PH	proportional hazards
PK	pharmacokinetic
PRO	patient reported outcome
PT	preferred term
PTAB	Patient Treatment Administration Burden
Q1	First quartile
Q3	Third quartile
Q12W	Once every 12 weeks
Q24W	Once every 24 weeks
QLQ-C30	Quality of Life Questionnaire-30 (items)
QLQ NMIBC24	Quality of Life Questionnaire Non-Muscle Invasive Bladder Cancer 24 (items)
QT	time from the beginning of the QRS complex to the end of the T wave
QTc	QT interval corrected for heart rate
QTcF	QT corrected for heart rate using Fridericia's formula
QTcB	QT corrected for heart rate using Bazett's formula
RCI	repeated confidence interval

Abbreviation	Term
RNA	ribonucleic acid
RMST	restricted mean survival time
ROW	rest of world
SAE	serious adverse event
SAP	statistical analysis plan
SC	subcutaneous
SD	standard deviation
SOC	system organ class
SRP	safety review plan
T1	stage of cancer in which the cancer cells are only growing in the most superficial layer of tissues and have not grown into deeper tissues; in bladder cancer, T1 is defined as an invasion into the lamina propria without invasion into the muscularis propria
Ta	stage of bladder cancer defined as a non-invasive papillary carcinoma
TBILI	total bilirubin
TEAE	treatment-emergent adverse event
TSQ	Treatment Satisfaction Questionnaire
TURBT	transurethral resection of the bladder tumor
UK	United Kingdom
ULN	upper limit of normal
US	United States
VAS	visual analog scale
WBC	white blood cell
